In addition to the oncological outcome, the neurological outcome is also very important. Depending on the localization of the tumor, its form and compression of intra-spinal structures such as the spinal cord or nerve roots many patients develop neurological deficits. Besides GTR the other goal of resection is the neurological recovery of these patients. Previous reports show that the time point of surgery is important in order to achieve full recovery (Schwake et al., 2018). However, most of the data is derived from retrospective case series. One of the aims of this registry is to prove this hypothesis. These neurological deficits are, as mentioned above, related to the localization of the tumor within the spine, Tumors in the cervical spine would cause mainly gait ataxia, spasticity, and weakness in the upper extremities while tumors in the lumbar spine would lead to deficits in the lower extremities in combination to disturbances of bladder, bowel, and sexual functions. These functions should be evaluated and monitored, before and after treatment.

Other concerns are safety requirements in order to prevent peri-operative complications. For example, the role of intra-operative neurophysiological monitoring. Some authors recommend the utilization intra operative monitoring, however, the evidence level is very low (Jesse et al., 2022; Thakur et al., 2021). Other open questions are for example the utility of microscope, methods for dura closure and thrombosis prevention.

On the other hand, some tumors can be treated with irradiation, some studies showed efficacy of this method mainly in the case of Schwannomas and meningiomas. In case of residual tumor or tumor progression irradiation can be also performed to prevent further growth (Chang & Lee, 2013).

Lastly, in comparison to the methods mentioned above, a wait-and-see approach can be used for asymptomatic patients or those with mild symptoms. In this case, clinical and imaging examinations are performed at regular intervals to check the neurological status and the tumor. This can also be done for longer periods of time because of the benign nature of these tumors with the slow growth. in case of new neurological deficits or progression surgical treatment should be advocated. Overall, it is not certain at what point therapy is indicated, especially in asymptomatic patients. Because many of these tumors are discovered by coincidence during imaging, which was performed due to other symptoms.

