11.4 Modified Japanese Orthopedic Association (mJOA) score (Tetreault et al., 2017)

mJOA Scoring Criteria (18-point version)

Upper Extremity Motor Dysfunction (max score: 5)

0: I am unable to move my hands at all

1: I can move my hands a little, but I am unable to feed myself

2: I can feed myself but, I am unable to button my shirt

3: I can button up my shirt, but I find it very difficult and it takes a long time

4: I can button my shirt with only slight difficulty

5: My hands work normally

Lower Extremity Motor Dysfunction (max score: 7)

0: I am paralysed and unable to move or feel my legs

1: I can feel my legs but I am unable to move them at all

2: I can move my legs but I cannot walk

3: I can walk but I require a walking aid

4: Able I can walk up and down stairs, but I have to hold the handrail

5: I am a little unsteady on my feet, but I can walk up and down stairs without holding the handrail

6: I am a little unsteady, but I can walk unaided

7: My legs are unaffected

Sensory Dysfunction of Upper Extremity (max score: 3)

0: I am unable to feel my hands

1: I have pain or severe loss of feeling (including numbness, tingling) in my hands

2: I have mild loss of feeling (including numbness, tingling) in my hands

3: I have no loss of feeling in my hands

Sphincter function (max score: 3)

0: I cannot control when I pass urine

1: I have marked difficulty passing urine

2: I have mild difficulty passing urine

3: I have no difficulty passing urine

Score Interpretation

15-17: Mild myelopathy

12-14: Moderate myelopathy

0-11: Severe myelopathy

11.5 bladder, bowel, and sexual functionality

Sensation in the “saddle” area (buttocks, medial hips)

- Normal
- Paresthesia
- Reduced sensation
- Absent sensation

Bladder function:

- Normal function
- Mild dysfunction (occasional incontinence, but mostly continent)
- Moderate dysfunction (frequent incontinence, but some control)
- Severe dysfunction (total incontinence)

Bowel function - Low Anterior Resection Syndrome (LARS) Score (Bittorf et al., 2003):

1. Incontinence for Flatus:

- Never: 0 points
- Less than once per week: 4 points
- At least once per week: 7 points
- Daily: 10 points

2. Incontinence for Liquid Stool:

- Never: 0 points
- Less than once per week: 3 points
- At least once per week: 7 points
- Daily: 13 points

3. Frequency of Bowel Movements:

- 1 time per day or less: 0 points
- 2-3 times per day: 4 points
- 4-6 times per day: 7 points

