- 7 or more times per day: 11 points

4. Clustering (Having multiple bowel movements in a short period):

- Never: 0 points
- Less than once per week: 9 points
- At least once per week: 11 points
- Daily: 13 points

5. Urgency (Sudden need to defecate):

- Never: 0 points
- Less than once per week: 11 points
- At least once per week: 16 points
- Daily: 18 points

Interpretation of Total Score:

- No LARS (0-20 points): Indicates normal or near-normal bowel function.
- Minor LARS (21-29 points): Indicates minor bowel dysfunction that may occasionally impact daily activities.
- Major LARS (30-42 points): Indicates significant bowel dysfunction with frequent symptoms that substantially impact daily life and quality of life.

Sexual functions

Male

- Normal erectile and ejaculatory function
- Mild erectile or ejaculatory dysfunction (able to have intercourse with mild difficulty)
- Moderate erectile or ejaculatory dysfunction (intercourse possible with significant difficulty or partial erection)
- Severe erectile or ejaculatory dysfunction (intercourse rarely or not possible)
- Complete loss of erectile and ejaculatory function

Female

- Normal sexual function
- Mild dysfunction (decreased arousal or lubrication, but able to have intercourse)
- Moderate dysfunction (significant difficulty with arousal or lubrication, painful intercourse)
- Severe dysfunction (intercourse rarely or not possible due to dysfunction)
- Complete loss of sexual function

11.6 Hospital Anxiety and Depression Scale (HADS) score (Stern, 2014):

Tick the box beside the reply that is closest to how you have been feeling in the past week.

Don't take too long over your replies: your immediate is best.

Don't take too long over your replies. Your immediate is best.

D	A	I feel tense or 'wound up':	D	A	I feel as if I am slowed down:
3		Most of the time	3		Nearly all the time
2		A lot of the time	2		Very often
1		From time to time, occasionally	1		Sometimes
0		Not at all	0		Not at all
		I still enjoy the things I used to enjoy:			I get a sort of frightened feeling like 'butterflies' in the stomach:
0		Definitely as much	0		Not at all
1		Not quite so much	1		Occasionally
2		Only a little	2		Quite Often
3		Hardly at all	3		Very Often
		I get a sort of frightened feeling as if something awful is about to happen:			I have lost interest in my appearance:
3		Very definitely and quite badly	3		Definitely
2		Yes, but not too badly	2		I don't take as much care as I should

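### The printed bowel key can label a patient with daily liquid-stool incontinence as normal or minor, never asks about solid stool, and has points that do not fit its bands

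*Protocol*

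**What the plan says.** The synopsis and Section 2.3 (Aims) list a questionnaire on bladder, bowel and sexual function among the secondary patient-reported outcomes. Section 2.1 names disturbance of these functions as a deficit of lumbar tumours and adds: "These functions should be evaluated and monitored, before and after treatment".

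The only bowel instrument shown is the LARS score in Section 11.5. It has five items: flatus incontinence, liquid-stool incontinence ("2. Incontinence for Liquid Stool"), frequency, clustering and urgency. No item covers solid stool. The key has three bands:

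- The lowest reads "No LARS (0-20 points): Indicates normal or near-normal bowel function".
- The middle reads "Minor LARS (21-29 points): Indicates minor bowel dysfunction that may occasionally impact daily activities".
- The highest runs from 30 to 42 points.

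Neither Section 6 (Statistics) nor the outcome lists say whether the items, the total or the band will be analysed.

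**The concern.** The protocol prints the items, the points, the bands and a verbal meaning for each band, so it fixes a rule for turning answers into a label. For some answers the label contradicts what the patient reported: loss of liquid stool every day can be read as near-normal function. The ordering can also reverse, with a fully continent patient scoring worse than one who is incontinent every day. Loss of solid stool adds nothing to the score, because it is not asked.

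The registry's stated rationale (Section 2.2) is to set benchmarks for functionality and neurological outcome. If the bowel result were reported as a LARS total or category, some incontinent patients would count as normal. A solid-stool answer that is not collected at admission cannot be reliably rebuilt later.

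**Working it through.** **Inputs (Section 11.5, printed points)**

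| Item | Never, or lowest frequency | Second level | Third level | Highest level |
|---|---|---|---|---|
| Flatus incontinence | 0 | 4 | 7 | 10 |
| Liquid-stool incontinence | 0 | 3 | 7 | 13 |
| Frequency | 0 | 4 | 7 | 11 |
| Clustering | 0 | 9 | 11 | 13 |
| Urgency | 0 | 11 | 16 | 18 |

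The top entries for the first three items are "Daily: 10 points", "Daily: 13 points" and "7 or more times per day: 11 points". Clustering starts at "Less than once per week: 9 points". Bands: 0–20 none, 21–29 minor, 30–42 major. Total = sum of the five items.

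**Step 1. Does the printed range reproduce?** No. Maximum total = 10 + 13 + 11 + 13 + 18 = 65, but the bands end at 42. Of the 4^5 = 1024 answer patterns, 305 total more than 42 and have no band.

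**Step 2. Totals for incontinent patients without urgency or clustering**

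- Daily liquid stool only: 13, lowest band.
- Plus flatus less than weekly: 13 + 4 = 17, lowest band.
- Plus flatus at least weekly: 13 + 7 = 20, lowest band.
- Plus 2–3 movements a day: 13 + 4 = 17, lowest band.
- Plus 4–6 movements a day: 13 + 7 = 20, lowest band.
- Liquid stool at least weekly with daily flatus: 7 + 10 = 17, lowest band.
- Daily liquid stool with daily flatus: 13 + 10 = 23, minor.

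Over the 4 × 4 = 16 flatus-by-frequency combinations with daily liquid-stool incontinence and no urgency or clustering, 5 fall in the lowest band, 8 in minor and 3 in major.

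**Step 3. How far the problem reaches.** All patterns with daily liquid-stool incontinence number 4^4 = 256: 5 lowest, 21 minor, 89 major, 141 above 42. So 5 + 21 = 26 fall in the two lower bands and 89 + 141 = 230 score 30 or more.

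- With any urgency (192 patterns): 0 lowest, 4 minor.
- With any urgency and any clustering (144 patterns): none in either lower band. The smallest total is 13 + 9 + 11 = 33.

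**Step 4. Rank order.** A patient with no incontinence, urgency less than weekly (11), clustering less than weekly (9) and 2–3 movements a day (4) scores 11 + 9 + 4 = 24. That exceeds the 23 of the patient with daily incontinence for both flatus and liquid stool. Of the 4^3 = 64 patterns without incontinence, 38 exceed 23; 34 of those 38 combine urgency and clustering.

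**Step 5. Weights.** Urgency outweighs liquid-stool incontinence at every level (11 v 3, 16 v 7, 18 v 13). Clustering outweighs it at the two lower levels (9 v 3, 11 v 7) and equals it when daily (13 = 13).

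All counts are of answer patterns. The documents give no distribution of answers, so they are not patient proportions.

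**The case against.** The strongest reply is that nothing in the protocol makes the LARS total or band the endpoint. The outcome is named only as a questionnaire, and the choice between items, total and band can be left to an SAP. Other routes would also show a deficit:

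- The liquid-stool answer is recorded by frequency.
- With other answers unchanged, new liquid-stool incontinence raises a patient's total by 3, 7 or 13 points, so a before/after comparison of totals would register it.
- The flow chart schedules cauda symptoms at admission, discharge, 3 and 12 months.
- Section 11.5 records saddle sensation.
- Adverse events are graded by CTCAE, and Section 2.4.5 lists bowel and bladder dysfunction.

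This stands against some stronger readings. A reader might infer that postoperative faecal incontinence is hidden, or that the registry will count incontinent patients as normal. The documents do not support either; masking arises only if the total or label serves as the result. A reader might also infer that daily liquid-stool incontinence is generally labelled normal or minor, but 230 of 256 patterns score 30 or more. Nor does daily clustering outweigh daily liquid-stool incontinence.

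It might further be argued that sacral-root lesions typically cause stool loss without urgency, so the failing patterns would be common here. The documents neither state this nor give a frequency, so it remains an assumption.

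A last objection is that every total rests on points that do not fit the bands. That is right. If the points are the misprint, the totals and the reversal must be recalculated. Moving the band limits alone would leave the reversal, because 24 exceeds 23 whatever the limits.

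The reply does not dispose of the key: its totals and bands are the only summary printed for these items, and its labels can contradict the answers. None of the other routes supplies a patient-reported solid-stool item in the questionnaire as printed.

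**Conclusion.** The point holds in a limited form. As printed, the key can place daily liquid-stool incontinence in the normal or near-normal band (13 to 20 points) or the minor band (for example 23) when urgency and clustering are absent or nearly so. It can also rank a continent patient (24) as worse. Solid-stool incontinence has no item. The consequence is conditional on the total or band being used as the bowel result, which the protocol leaves open.

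The mismatch between a maximum of 65 and bands ending at 42 does not depend on that condition. The points and bands cannot belong to the same scoring, and the documents do not show which is wrong. All totals above assume that the points are as printed.

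This concerns one component of one secondary questionnaire and does not touch the primary outcomes. It is worth correcting early because the solid-stool answer needs an admission value.

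**What to change.** 1. Reconcile the printed points and bands against the score's source, and correct Section 11.5 and the eCRF, before any total or label is used.
2. State that the band label alone is not the bowel outcome.
3. Report liquid-stool incontinence directly from the existing item: the share of patients with it at least weekly at each visit, and the change from admission.
4. Add one solid-stool incontinence line to the eCRF with the same four frequency answers, collected from admission onward.

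An override that forces incontinent patients into a higher band is not advised. It would be an unvalidated rule on a key that first needs reconciling.

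The cost is one extra eCRF line and a short outcome definition. The LARS total becomes descriptive.

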	
Primary Outcome
 
 • Quality of life based on the questionnaire (EQ-D5) • Extent of tumor resection (see CRF): 
 according to surgeon: 
 1. Meningioma: Simpson grade 1 and 2 2. Schwannoma: complete resection, including nerve root 3. Cauda ependymoma: complete resection, including filum terminale according to postoperative MRI, 3 months after surgery 4. Other: surgeon's decision • Neurological status (McCormick Score) (see CRF), 3 months after surgery
Outcome(s)	
Secondary Outcome
 
Imaging: preoperative and postoperative MRI (3 months) according CRF
 
 • Volumetry • Spinal canal occupancy ratio in % 
Further patient reported outcomes:
 
 • Functionality: Neck disability index (NDI) for tumors in the cervical spine, Oswestry disability index (ODI) for tumors in the thoracic and lumbar spine (see CRF) • Local and radicular pain (VAS 1-10) (see CFR) • Neurological status: motor function of each limb, ataxia and gait (mJOA score) (see CRF) • HADS score- based score for anxiety • Questionnaire on bladder, bowl, sexual functionality

	
Quality indicators (QI):
 
Length of hospital stay
 
30- and 90-days readmission
 
Nosocomial infections
 
Blood loss
 
Duration of surgery
 
Progression of the disease or recurrence
 
Other adverse events
 
Mortality
 
Assessment of adverse events according to Common Terminology Criteria for Advers Events (CTCAE) 5.0 and severity according to the Ibañez scale (see CRF)
 
CSF leakage is defined as one, when CSF leakage is identified on imaging of clinically and treatment is required: operative or conservative (Lumbar drain for example)
 
Postoperative kyphosis or deformity is defined, when symptomatic (for example pain) or evident on imaging (for example kyphotic fracture on MRI)

Study design	Registry trial
Statistical analysis	
Primary Outcome
 
Improvement of neurological function, quality of life, and extent of resection
 
Secondary Outcome
 
Descriptive data analysis of clinical parameters is performed. Confidence intervals for relevant treatment effects are calculated using univariate and multi-variate statistical tests

Number of cases	100 patients
Time period	February 2025 until June 2027
Number of centers	N= X

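### The bowel (LARS) items in Protocol section 11.5 add up to 65 points, but the key for the total ends at 42, so the most symptomatic patients have no category

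*Protocol*

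**What the plan says.** The Synopsis lists among the secondary patient-reported outcomes a "Questionnaire on bladder, bowl, sexual functionality", and section 2.3 (Aims) repeats it. Section 2.1 says of bladder, bowel and sexual function: "These functions should be evaluated and monitored, before and after treatment".

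Section 11.5 supplies the bowel instrument, named as the LARS score, with a reference beside the name. It has five items with four answers each. The highest answers carry these points:

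- flatus incontinence: "Daily: 10 points"
- liquid stool incontinence: "Daily: 13 points"
- stool frequency: "7 or more times per day: 11 points"
- clustering: 13 points, again for the daily answer
- urgency: "Daily: 18 points"

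The key for the total follows directly. It has three bands: No LARS for 0-20, then "Minor LARS (21-29 points): Indicates minor bowel dysfunction that may occasionally impact daily activities", then "Major LARS (30-42 points): Indicates significant bowel dysfunction with frequent symptoms". Nothing is said about totals above 42.

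**The concern.** A key for a summed score should cover every total that the items can produce. This one stops well short of the sum of the item maxima, so either the points or the bands are misprinted, or they come from different versions of an instrument.

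If the table is applied as printed, two things follow. Patients with the most frequent symptoms get a total that no band covers. And because the cut-offs at 21 and 30 may not suit these points, a band's description can disagree with the answers behind it. Any before-and-after table by LARS class would lose patients at the severe end. The comparison with historical cohorts announced in section 6.2 could not rest on classes assigned in this way.

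**Working it through.** **Inputs (Protocol section 11.5)**

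| Item | Points for the four answers, mildest to worst |
|---|---|
| Flatus incontinence | 0, 4, 7, 10 |
| Liquid stool incontinence | 0, 3, 7, 13 |
| Bowel movements per day (at most 1; 2-3; 4-6; 7 or more) | 0, 4, 7, 11 |
| Clustering | 0, 9, 11, 13 |
| Urgency | 0, 11, 16, 18 |

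Except for stool frequency, the answers run never, less than once per week, at least once per week, daily. Bands: 0-20, 21-29, 30-42.

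**Step 1: the maximum.** The key implies a maximum of 42. The items give 10 + 13 + 11 + 13 + 18 = 65, so the stated figure is not reproduced; the gap is 65 − 42 = 23 points.

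**Step 2: every answer combination.** There are 4^5 = 1,024. Summing the points and applying the printed bands:

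| Band | Combinations |
|---|---|
| 0-20, No LARS | 98 |
| 21-29, Minor | 190 |
| 30-42, Major | 431 |
| Above 42, no band | 305 (29.8%) |
| Total | 1,024 |

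Of the 66 whole numbers from 0 to 65, only 1, 2, 5, 6 and 64 cannot be reached, which leaves 61 attainable totals. Those above 42 are 43 to 63 (21 values) and 65, so 22 totals have no category.

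**Step 3: who falls outside the key.** Adding 0, 4, 7 or 11 for stool frequency:

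- All four symptoms daily: 10 + 13 + 13 + 18 = 54, giving 54, 58, 61 or 65. None is classified.
- All four at least weekly, but none daily: 7 + 7 + 11 + 16 = 41, giving 41, 45, 48 or 52. Only the first is classified, as Major.
- All four either at least weekly or daily: 2^4 × 4 = 64 combinations. Raising any one symptom from 41 to daily adds at least 2 points, and any higher stool frequency adds at least 4, so 63 of the 64 exceed 42.

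A patient with all four symptoms at least weekly who goes from at most one movement per day to 2-3 thus moves from 41 (Major) to 45 (no band).

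**Step 4: labels against answers.**

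- All four symptoms less than weekly: 4 + 3 + 9 + 11 = 27, giving 27, 31, 34 or 38. With 2-3 movements per day the total is 31, which is Major; with at most one it is 27, which is Minor.
- Daily flatus and daily liquid stool incontinence, no clustering or urgency: 10 + 13 = 23 with at most one movement per day and 27 with 2-3. Both are Minor.
- Of the 2^4 × 4 = 64 combinations in which no symptom is more frequent than less than weekly, 8 reach the Major band (30 to 38). Seven of these need 4 or more movements per day; the eighth is the 31-point case.

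**The case against.** The sum of 65 against 42 is hard to dispute. The item lists are complete and in rising order, so this is not damage from text extraction. The serious objections concern how much it matters.

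- **The labelling examples are weaker than the gap.** In a weighted sum, several mild items can outrank one severe item, and that alone is no error. Seven of the eight low-frequency Major cases have 4 or more movements per day, which is itself a scored symptom. This stands: the examples illustrate the mismatch, and the proof is the missing band.
- **No section says that LARS class will be analysed.** The protocol lists only a questionnaire, and section 6.2 speaks of historical cohorts in general terms. This also stands, so the consequence is conditional on reporting by class. Still, the protocol prints the bands for some use, and an analysis plan that adopts them inherits the contradiction.
- **Totals above 42 could simply be read as Major.** The protocol does not say so. Doing so would also assume that the lower cut-offs suit a 65-point item set, which is exactly what is in doubt.
- **A source is already cited.** True: section 11.5 refers to a study of anastomotic leakage and function after rectal resection for cancer. Whether it contains this scale cannot be checked from the protocol, so the reference belongs in the correction.
- **The CRF is not shown.** The error may be confined to the appendix. That limits the possible harm but does not remove the contradiction.

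**Conclusion.** The concern holds. The printed points and the printed key contradict each other: the maximum is 65, the key ends at 42, and 22 of 61 attainable totals have no category. The gap lies where symptoms are most frequent. The protocol shows that points and key disagree, not which of them is wrong.

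The counts describe answer combinations, not patients. The protocol gives no bowel-symptom frequencies, so neither the number of unclassified patients among the planned 100 nor the net effect on the rate of Major LARS can be estimated. The consequence assumes that the table is applied as printed and that results are reported by class. Item answers and summed totals can still be compared before and after surgery, and primary outcomes, sample size and safety are not affected. It should be fixed, but it does not threaten the study.

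**What to change.** 1. Check the item wording, answer categories, points and cut-offs in section 11.5 against the instrument's source, and confirm or correct the reference given there. All parts should come from one scale, with every attainable total in exactly one category.
2. If the (e)CRF scores this item set, make its scoring match the corrected table.
3. Store the item-level answers, not only the total or class.
4. Re-score records already collected where their answer categories match the corrected version; where they do not, set the LARS class to missing.

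The cost is the correction of one appendix table and, if needed, of the eCRF scoring. No extra patients or visits are required. Correcting it early is cheaper, because answers collected in the wrong categories may not be re-scorable.
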